14.3 Sample Size and Power

We plan to accrue 60 participants in the pilot trial. A sample size of 30 per arm is consistent with the NIDA Stage Model of behavioral treatment development, which suggests that pilot trials should include approximately 15-30 participants per arm for preliminary evaluation of the intervention [36].

14.4 Randomization

Following the completion of the baseline and contact information survey the participant will receive a text message with a link. Once this link is clicked an automated algorithm will randomize participants 1:1 to either the ACT on Vaping or the assessment-only control arm. The randomization algorithm will use a permuted-block

design with random block sizes, with stratification by high (>5) vs. low (5 or less) readiness to quit on the Contemplation Ladder [56]. Only the unblinded study biostatistician will have access to treatment assignment. Although we project, based on our previous work [28], that the majority of outcome assessments will be completed via web-based survey, any outcome evaluator who has direct contact with participants will remain blinded to treatment group assignment until the final set of questions regarding acceptability of the ACT on Vaping intervention.

14.5 Missing Data

Participants with missing tobacco use data will be considered non-abstinent [73] in the primary analysis. We will also report the results of sensitivity analyses using complete case analysis of those providing follow-up data. If there is a substantially differential rate of missing data (either self-report or cotinine analytic results) across arms, we will use complete case analysis in the primary outcome analysis instead of missing=tobacco use.

14.6 Ethnic and Gender Distribution Chart

Projected Target Accrual
ETHNIC AND GENDER DISTRIBUTION CHART

TARGETED / PLANNED ENROLLMENT: Number of Subjects			
Ethnic Category	Sex / Gender		
	Females	Males	Total
Hispanic or Latino	3	2	5
Not Hispanic or Latino	28	27	55
Ethnic Category Total of All Subjects*	31	29	60
Racial Categories			
American Indian / Alaska Native	1	1	2
Asian	1	1	2
Native Hawaiian or Other Pacific Islander	0	0	0
Black or African American	2	1	3
White	25	24	49
More Than One Race	2	2	4
Racial Categories: Total of All Subjects*	31	29	60

15.0 INVESTIGATOR OBLIGATIONS

The PI is responsible for the conduct of the clinical trial at the site and is responsible for personally overseeing the treatment of all study participants. The PI must assure that all study site personnel, including sub-Investigators and other study staff members, adhere to the study protocol and to all applicable regulations and guidelines regarding clinical trials both during and after study completion.

All participants are informed of the nature of the program, its possible hazards, and their right to withdraw at any time, and each participant signs a form indicating their consent to participate prior to receiving any study-related procedures.

16.0 POST-TRIAL USABILITY STUDY

Objectives:

Conduct a diary study with young adults (n=10) to assess user satisfaction with the app and its components as well as program utilization (n=10) and additional modifications needed to continue with the ACT on Vaping app development in preparation for the future UH3 phase of this study.

16.1.1 Study Population

We will recruit 10 YA e-cigarette users, ages 18-30, who meet basic eligibility criteria for the trial described below.

Participants will be recruited nationally via one or more recruitment strategies used successfully in our previous studies (e.g, social media, targeted Craigslist ads).

16.1.2 Study Design

Following the completion of the clinical trial, we will conduct a diary study as a field-based evaluation of its usability. Usability is the extent to which a digital intervention can be easily navigated and understood by the user [52]. Usability is a critical outcome of the intervention development process, as low usability can undermine engagement with the intervention as well as its potential efficacy for tobacco cessation [53].

16.1.3 Primary Objective:

Continued development of the *ACT on Vaping* smartphone application for tobacco cessation based on ACT. The ACT on Vaping app will be easily navigated and understood by the user and free from any technical difficulties.

16.2 Estimated Accrual:

We estimate that our recruitment efforts will lead to:

- 120 screened, 40 eligible and 10 enrolled.

We estimate recruitment to take 2-3 weeks

16.3 Eligibility:

16.3.1 Inclusion Criteria

- age 18-30
- current weekly user of e-cigarette product(s)
- owns an Android phone or iPhone
- has an email address
- US resident, with a US mailing address
- willing to complete all study procedures
- comfortable reading and writing in English

16.3.2 Exclusion Criteria

[figure not shown]
- currently using other tobacco cessation treatments at the time of screening, including pharmacotherapy or behavioral support
- previous participation in a Fred Hutch vaping or smoking cessation study
- currently in prison
- member of the same household as another research participant
- Google voice number as sole phone number, due to its association with fraudulent study entry attempts

16.4 Registration

Potential participants will be recruited via social media (e.g. Facebook, Twitter). Initial screening for participation will be conducted via web-based survey. Individuals deemed eligible will be contacted by phone to ensure eligibility and discuss study procedures; individuals remaining eligible and interested will be invited to attend an online, video-based visit.

16.5 Diary Testing Overview

Figure 1. Usability Testing Study Flow Chart

During the online, video-based onboarding visit, participants will be provided with information about the study and provide verbal informed consent to participate. During that visit, study staff will assist enrolled participants in downloading ACT on Vaping to their personal phone (Android or iPhone). Participants will be instructed to use the program for 6 days and to keep a daily diary to report on their usage of and satisfaction with the program. Daily diaries will follow a semi-structured format, including assessments of when they used the app, what prompted them to open it, what features they accessed, and what their overall experience was like. They will also be asked about any technical difficulties encountered and about ease of navigation. Following completion of the diary entries, they will be asked to attend a final debriefing session which will include a semi-structured exit interview to assess (a) usage and satisfaction with the app, and (b) the impact of *ACT on Vaping* on their e-cigarette use.

These procedures are consistent with best practices and usability testing of government-funded cessation programs [52] and have been successfully implemented previously in our treatment development work. After the diary study, the UX Researcher will work with the team of investigators to use data gleaned from the diary study to inform any needed changes to ACT on Vaping's content and structure as well as to address any technical difficulties experienced by the users. The software development team will then make changes needed to improve the usability and/or content of the app in preparation for the UH3 phase of the trial.

16.6 Participant Compensation

Diary study participants will be compensated up to \$140 for completion all activities. Compensation will be pro-rated and dispersed as follows:

- \$10 for the baseline visit.
- \$10 for mid-point check in.
- \$40 for the final debriefing visit.
- \$10 for each daily diary entry, up to \$60 (for 6 days).
- \$20 bonus for completing all 6 diary entries.

16.7 Enrollment Procedures

Participants will be recruited nationally through online services (e.g., Facebook, Twitter advertisements). Recruitment materials will direct potential participants to a web-based screening survey. The survey provides

basic information about the study to allow individuals to choose whether or not to proceed, then assess basic eligibility criteria. Individuals who do not meet eligibility criteria will be provided with the following cessation resources via e-mail; the Smokefree.gov and the 800-QUIT-NOW phone number to reach their state's quitline.

Phone screening & informed consent:

Study staff will call individuals who are deemed potentially eligible based on the initial online screening. During this call, the purpose and procedures of the study will be explained in further detail and key eligibility criteria will be re-assessed to ensure consistency of answers. Those who remain eligible and interested will be invited and scheduled for the online onboarding meeting. Study staff will email the study information sheet to the individual to review before the online meeting.

Diary Study onboarding video meeting. We will email participants the information needed to access the online meeting, which will be conducted and recorded via video conference. The onboarding meeting will be conducted by the UX researcher and will last approximately 30 minutes. The study consent will be reviewed and discussed first, and participants will be asked to provide verbal consent before proceeding. During the onboarding meeting, participants will be given password-protected access to the *ACT on Vaping* app and will receive assistance with downloading the app. During this meeting, participants will also be asked about their motivation to quit vaping. The brief (10-15 minutes) mid-study session call and the final exit interview will also be scheduled. After the onboarding meeting, study staff will email participants their log-in credentials for the *ACT on Vaping* app as well as the date and time of their mid-study feedback call and their final exit interview.

16.8 Assessments/Evaluations

Onboarding video call (Day 1): Vaping level, motivation (importance and confidence) to change vaping habits and cost of vaping will be assessed.

Daily diary entry (Days 2-7): Participants will be instructed to use *ACT on Vaping* app for 6 days and to submit a daily diary to report on their usage of and satisfaction with the program. Daily diaries will follow a structured format, including assessments of when they used the app, what prompted them to open it, what features they accessed, and what their overall experience was like. They will also be asked about the specific device and operating system they used to access the app, any technical difficulties encountered and about ease of navigation.

Mid-study check in call (Day 3-4): the UX Researcher will connect briefly with each participant for a 10-15-minute check in about their experience and engagement with the *ACT on Vaping* app. Qualitative research notes will be taken during this call.

Final exit interview (Day 8): Following completion of the diary study, participants will be asked to attend an online video meeting for a final debriefing session which will include a semi-structured exit interview to assess (a) usage and satisfaction with the app, and (b) the impact of *ACT on Vaping* on their e-cigarette use and engagement with the app. Participants will also be asked to report any technical difficulties they may have experienced.

16.9 Analytical methods

Qualitative data from diary entries and exit interviews will be coded and analyzed using rapid inductive content analysis to extract themes.

16.10 Continued Intervention Development

The data gleaned from the diary study will inform any needed changes to *ACT on Vaping* app's content and structure as well as to address any technical difficulties experienced by the users.

The Moby Inc. programming team will then make changes needed to improve the usability and/or content of the app and will complete additional modifications to the *ACT on Vaping* program based on participant feedback. The next version of *ACT on Vaping app*, that will be developed after the diary study, will be used in the future (UH3) phase of this study.

1.1 Brief description of the protocol

This study will adapt a digital Acceptance and Commitment Therapy (ACT) program into an app-based digital therapeutic for young adult (YA) vaping cessation and evaluate its preliminary acceptability and efficacy relative to an incentivized text message control condition.

1.2 The primary aims are:

Aim 1 (Y1-Y2). Develop the ACT on Vaping smartphone app and evaluate its acceptability and preliminary impact on cessation-related targets.

- 1.a. Gather input from users and subject matter experts (YAs who vape, team members with expertise in YA vaping) to develop vaping-focused content for the novel program.
- 1.b. Complete Q-submission to obtain FDA feedback on the regulatory pathway for the intervention.
- 1.c. Conduct a pilot RCT (n=60) to evaluate acceptability and preliminary efficacy of ACT on Vaping relative to an incentivized text message control condition.

Aim 1 outcomes will be evaluated using the following go/no-go criteria to determine whether proceeding to a larger UH3-phase study is warranted: (a) Completed FDA Q-submission. (b) From the pilot trial, evidence that ACT on Vaping is acceptable (overall satisfaction averaging at least 3.5 out of 5) and produces better outcomes than the control intervention on at least 1 of 3 efficacy endpoints: change in readiness to quit (mean difference in Contemplation Ladder change scores ≥ 1), 24-hour quit attempts ($\geq 5\%$ difference), and cotinine-confirmed 30-day point prevalence abstinence from all nicotine/tobacco products at 3 months ($\geq 5\%$ difference).

1.3 Primary outcome measures

Type	Name	Time Frame	Brief Description
Primary	Overall treatment satisfaction rating	3 months post-randomization	Satisfaction with the assigned intervention on a 5- point Likert-type scale
Primary	Change in Contemplation Ladder scores from baseline	3 months post-randomization	Change in readiness to quit using e-cigarettes
Primary	Self-reported 24-hour quit attempt	3 months post-randomization	Proportion of participants making a quit attempt lasting at least 24 hours between baseline and 3- month follow-up
Primary	Cotinine-confirmed 30-day point prevalence abstinence from all nicotine and tobacco	3 months post-randomization	Biochemically confirmed 30-day abstinence from all nicotine and tobacco products at follow-up (excluding FDA-approved pharmacotherapies)

1.4 Inclusion/exclusion criteria

Inclusion Criteria

- age 18-30
- current weekly user of e-cigarette product(s) for the last 30 days
- has a smartphone either an Android (running version 10.1 or higher) or iPhone (running iOS version 13 or higher)
- experience downloading and using one or more apps on their smartphone
- have a mobile data plan and/or access to WiFi to support the use of the ACT on Vaping app
- has access to text messaging
- has an email address
- US resident, with a US mailing address
- willing to complete all study procedures
- comfortable reading and writing in English

Exclusion Criteria

- currently using other tobacco cessation treatments at the time of screening, including pharmacotherapy or behavioral support (note: use of these treatment is allowable during trial participation)
- member of the same household as another research participant
- currently in prison
- Google voice number as sole phone number, due to its association with fraudulent study entry attempts
- is ineligible per fraud prevention protocol
- employees/family of investigator or study center

1.5 Power calculation and sample size

Sample size determination. We plan to accrue 60 participants in the pilot trial. A sample size of 30 per arm is consistent with the NIDA Stage Model of behavioral treatment development, which suggests that pilot trials should include approximately 15-30 participants per arm for preliminary evaluation of the intervention [1].

1.6 Schedule of assessments

Measure	# items	Screening Survey	Baseline Survey	3-mo. Follow-up Survey	Primary Purpose
Eligibility criteria	11	X			Eligibility
Demographics	10		X		Sample description
e-FTCD (severity of dependence)	6		X	X	Sample description
Tobacco/nicotine use history	9		X		Sample description
Contemplation Ladder (readiness to quit)	1		X	X	Primary outcome
Recent tobacco/nicotine use	3		X	X	Primary outcome
Saliva cotinine	n/a			X	Primary outcome
Outside tobacco treatment	2		X	X	Concomitant treatment
Treatment satisfaction	8			X	Primary outcome
Treatment adherence (tracked automatically)	n/a			X	Primary outcome

Abstinence self-efficacy	1		X	X	Exploratory
AIS cravings subscale (psychological flexibility)	9		X	X	Exploratory
Valuing Questionnaire (psychological flexibility)	10		X	X	Exploratory
Past 30-day alcohol and cannabis use	2		X	X	Exploratory
Agent Persona Instrument (avatar perceptions)	25			X	Exploratory
Adverse events	1			X	Safety monitoring
Total number of items		11	62	73	
Estimated duration (mins)		5-10	30-35	35-40	

2 Trial Management

2.2 Projected timetable for the pilot RCT

Based on previous trials that used a similar national recruitment strategy (ranging from 78-862 randomized/month), we estimate enrollment of at least 120 participants/month, requiring a recruitment period of less than 1 month for the UG3 phase (n=60).

2.3 Target population distribution

We will actively seek participants who are diverse in their gender identity, including people who identify as cisgender men and women and those who identify transgender and gender expansive. We will also make every effort to ensure that members of diverse racial/ethnic groups are adequately represented in the study by targeting our online recruitment efforts based on location (e.g. Craigslist ads in cities with a high proportion of racial/ethnic minority residents) and use of the Facebook advertising platform to target on user interests and affiliations. In previous studies we have achieved at least 25% minority participation in trials using these methods. In the most recent large trial of a web-delivered intervention [7], the sample was 27% racial minority and 8% Hispanic/Latino. In our EQUAL pilot study, 27% identified as racial/ethnic minority. Although the UG3 trial is not designed to ensure statistical power to evaluate effect moderators, we will program the recruitment website to ensure that at least 25% identify as racial/ethnic minority.

3 Data management and analysis

3.1 Data acquisition and transmission

Recruitment. Participants will be recruited nationally via recruitment strategies used successfully in previous studies conducted by our group: targeted Facebook ads; Craigslist ads in cities with a high prevalence of nicotine and tobacco use or racial/ethnic minority residence; other free methods of advertising on the Internet (e.g., Reddit, Twitter); ResearchMatch.org; and earned media generated by press releases from the Fred Hutch media team. Recruitment materials will direct potential participants to a recruitment website, which provides basic information about the study and a portal to screening survey. In order to ensure that at least 25% of the sample identifies as racial/ethnic minority, we will program the website to limit recruitment of those who identify as non-Hispanic White to 75% and continue recruitment until the racial/ethnic minority recruitment goal of at least 25% is reached. This similar to recruitment capping methods used in our other trials.

Informed Consent Procedures. Recruitment materials will direct potential participants to a secure recruitment website, which provides basic information about the study and a portal to the screening survey. For participants who screen eligible on the recruitment website and provide their email address, we will instantly send them an email and/or text message (and two reminders over a 7-day period) inviting them to provide informed consent and complete the baseline assessment. Those not consenting and completing or not eligible will be sent an email notifying them that they were not enrolled and providing both the link to Smokefree.gov and the 1-800-QUIT-NOW phone number for cessation support.

Sources of materials and app utilization data

The data relevant to the proposed project will be gathered strictly for research purposes. Data collected will be in the form of structured assessment instruments, app utilization data, and saliva cotinine test results.

Assessment instruments. Structured assessment instruments will be administered by web-based forms or by trained research staff in order to: (1) evaluate study eligibility and establish baseline characteristics of the sample, (2) evaluate study outcomes.

App utilization data. At randomization, participants assigned to the ACT on Vaping arm will be given a unique log-in ID to access their assigned app, which will serve as the link to the rest of their study data.

Saliva cotinine testing. Cotinine test kits will be shipped at each follow-up to all self-reported abstainers who have not used nicotine replacement therapy in the prior 7 days to biochemically verify nicotine and tobacco use status for the purpose of cessation outcome assessment. Participants will upload a photo of their test result using a secure web-based form.

3.2 Outcome data collection

Following our data collection protocol used in previous trials, we will collect email, phone number, and mailing address. The data collection protocol is as follows: Assessment Day -14: Mailed reminder of upcoming survey, with \$2 pre-incentive included; Day 0: First email and/or invitation with link to online survey; Day 5: Second email and/or text invitation with link to online survey; Day 9: Third email and/or text invitation with link to online survey; Days 10 to 18: Eight attempts to complete telephone version of survey (one call per day); Day 18: Send mailed version of survey; Participants will receive an incentive of \$50 the follow-up survey completed and an additional \$25 for returning cotinine results if asked. In addition, an extra incentive of \$10 will be provided to participants who respond to the first email and/or text invitation and complete the survey online within 24 hours. Based on previous trials using these same procedures [19, 28], we expect that 80% of participants will complete assessments via web-based survey, ~2% by phone, ~3-4% by mailed survey.

3.3 Data entry methods

All screening, baseline, and outcome survey data will be entered either directly by study participants who complete the online surveys or study staff (for participants who complete the surveys by phone or mail) into a study database managed by Datatope, LLC.

3.4 Data security and protecting confidentiality

Numerous safeguards will keep data secure. Each subject will be assigned a code number so that, should any non-study personnel gain access to the data, they will not know to whom they belong. Any hard copy data will be kept in a locked file cabinet accessible only by authorized research staff. A secure password is required to access computers at each site, and computer networks are on secured servers that meet or exceed federal confidentiality standards. Once randomized into the ACT on Vaping arm, each participant will have access to their assigned app protected with a login. All connections will be made using the secure sockets layer (SSL).

Participant data are maintained on a server in a locked server room at Fred Hutch. Full access to the server is restricted to two staff members of the Fred Hutch Public Health Sciences Information Technology (PHS-IT) group and the two developers of the study management system.

3.5 Data analysis plan

To address Sex as a Biological Variable, we will explore whether outcomes described below are associated with sex assigned at birth. If they are, that variable will be added to the relevant models. Primary analyses will be conducted as described below:

To evaluate the go/no-go criteria for the pilot trial, we will calculate descriptive statistics (e.g., means, proportions) for the ACT on Vaping treatment group to assess treatment satisfaction (i.e., mean level of overall satisfaction with ACT on Vaping, with 3.5 on a 5-point scale being the “go” criterion). For the three cessation related-outcomes, we will evaluate differences descriptively to determine whether ACT on Vaping showed evidence of better outcomes on at least 1 of 3 efficacy endpoints as the final “go” criterion: change in readiness to quit (mean difference in Contemplation Ladder change scores ≥ 1), 24-hour quit attempts ($\geq 5\%$ difference), and cotinine-confirmed 30-day point prevalence abstinence from all nicotine/tobacco products at 3 months ($\geq 5\%$ difference). Given that pilot and feasibility trials are not appropriate designs for testing hypotheses regarding the efficacy of interventions [5, 6], we will focus on descriptive differences as an alternative to hypothesis testing. Similarly, since a single effect size derived from a small sample is an inherently unreliable estimate of the true intervention effect size [6], we aimed to reduce the likelihood of early abandonment of a potentially promising treatment by requiring evidence of a clinically meaningful effect on one of three cessation-related outcomes as the “go” criterion for efficacy.

Missing data. Participants with missing nicotine use data will be considered non-abstinent [6] in the primary analysis. We will also report the results of sensitivity analyses using complete case analysis of those providing follow-up data. If there is a substantially differential rate of missing data (either self-report or cotinine analytic results) across arms, we will use complete case analysis in the primary outcome analysis instead of missing=vaping/smoking.

4 Quality assurance plan

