We developed a digital Acceptance and Commitment Therapy (ACT) program designed for YA cigarette smokers aged 18-30 at all stages of readiness to quit. ACT's overarching focus on increasing psychological flexibility offers a new approach for YAs to motivate and support cessation, and ACT may have better efficacy than standard care approaches for tobacco cessation. The program also employs another exciting innovation: an avatar guide to make the program more engaging and effective. The original program, called Flexiquit, showed promise in motivating smoking cessation in a pilot randomized controlled trial (RCT) with YAs in Cyprus, with a 29% self-reported posttreatment quit rate for Flexiquit vs. 11% for waitlist control. Our single-arm pilot results with US sexual and gender minority YAs who smoke cigarettes were similarly promising: 93% satisfaction and a 23% biochemically confirmed quit rate at 2 months.

Overview of Study Design

In this study, we propose to evaluate the acceptability and efficacy of ACT on Vaping for young adult e-cigarette users in a 2-arm randomized controlled pilot trial (n=60 total with 1:1 allocation to the two treatment arms). The primary aim is to develop the pilot trial-ready version of the ACT on Vaping program and evaluate its acceptability and preliminary efficacy for impacting cessation-related targets. We will test the intervention using a 3-months treatment period, and, consistent with the evaluation period in our previous cessation app pilot study, our primary outcomes will be assessed at the 3-months end-of-treatment mark.

- 1.1 Protocol Title:** ACT on Vaping: Development of a Digital Therapeutic for Young Adult Vaping Cessation
- 1.2 Sponsor Information:** National Institutes of Health, Grant Number: 1UG3DA057032
- 1.3 Investigator Information:**
[name]. [contact]
- 1.4 Contractors and Consultants for the Study (if applicable):**
[name]. (The University of Massachusetts and Edith Nourse Rogers Memorial Veterans Hospital)

[name]. (University of Cyprus, UCY)
 [name]. (Truth Initiative)
 [name]., (George Washington University)
 [name].
 [name], M.S., RAC (ENEM Consulting)
 Datatope LLC
 Moby Inc.

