4.1.1 Primary Endpoints

- Treatment acceptability as indicated by overall treatment satisfaction rating
- Treatment efficacy:
 - Change in Contemplation Ladder scores from baseline to 3-months post-randomization
 - Self-reported 24-hour quit attempt at 3-months post-randomization
 - Cotinine-confirmed 30-day point prevalence abstinence from all nicotine and tobacco at 3-months post-randomization

Trial go/no-go criteria for proceeding to a subsequent Phase II trial are: (1) satisfaction with ACT on Vaping averaging at least 3.5 out of 5; and, (2) relative to control, evidence of better outcomes on at least 1 of 3 efficacy endpoints: change in readiness to quit (mean difference in Contemplation Ladder change scores ≥ 1), 24-hour quit attempts ($\geq 5\%$ difference), and cotinine-confirmed 30-day point prevalence abstinence from all nicotine/tobacco products at 3 months ($\geq 5\%$ difference).

Efficacy benchmarks were based on clinically meaningful differences in Contemplation Ladder (ie., at least one-step change in average ladder score) or behavior change outcomes (5% difference in 24-hour quit attempts, 30-day PPA rates).

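### The only sensitivity analysis for missing abstinence data, complete case, cannot show whether the missing participants decide the verdict on the 5-point abstinence criterion

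*Combined protocol and SAP*

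**What the plan says.** The missing-data rule appears in protocol section 14.5 and again, in nearly the same words, in section 3.5 of the DSMP (Appendix A). The primary rule is: "Participants with missing nicotine use data will be considered non-abstinent". The only sensitivity analysis is: "We will also report the results of sensitivity analyses using complete case analysis of those providing follow-up data". If missing data, whether self-report or cotinine, differ substantially between arms, the roles change: "we will use complete case analysis in the primary outcome analysis instead of missing=vaping/smoking". No cut-off for a substantial difference is given. Neither section plans a tipping-point, best-case/worst-case or imputation analysis.

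The abstinence criterion (sections 4.1.1 and 14.2, DSMP 3.5) is an observed advantage of at least 5 percentage points in cotinine-confirmed 30-day abstinence. There is no test: "we will focus on descriptive differences as an alternative to hypothesis testing". On size, DSMP 1.5 says: "A sample size of 30 per arm is consistent with the NIDA Stage Model of behavioral treatment development". On follow-up, DSMP 3.2 says: "we expect that 80% of participants will complete assessments via web-based survey, ~2% by phone, ~3-4% by mailed survey".

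**The concern.** A sensitivity analysis for missing outcomes should change the assumption about those outcomes and show whether the conclusion moves. Here the primary rule fixes every missing participant as a user, and complete case leaves them out. The count of confirmed abstainers is the same in both, so the comparison cannot reveal what would follow if some of the missing had in fact been abstinent.

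The cut-off is coarse: one participant in an arm of 30 is 3.3 points against a 5-point criterion. The outcomes of a few missing people can therefore matter, and two agreeing analyses could be taken as evidence that they do not. Nor are the missing all of one kind. Cotinine kits go only to self-reported abstainers (sections 8.3.3 and DSMP 3.1), so anyone who lacks only a cotinine result has already reported abstinence.

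**Working it through.** **Inputs.** 30 per arm (14.3, DSMP 1.5); criterion of at least 5 points (4.1.1); expected response 80% + 2% + 3-4% = 85-86% (7.3, DSMP 3.2). That is 51-51.6 of 60 responding, or about 25-26 per arm, and 8.4-9 missing. The plan has no power or precision calculation to reproduce.

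**Notation.** a and c are the confirmed abstainers in the app and control arms, and r is the number of responders in each arm.

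**Step 1: equal response.**
- Missing = use: (a - c)/30 ≥ 0.05 requires a - c ≥ 1.5, so a lead of 2.
- Complete case: (a - c)/r ≥ 0.05 requires a - c ≥ 0.05r. For r = 21 to 30 this is 1.05 to 1.5, so again a lead of 2.

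Complete case multiplies the difference by 30/r (1.20 at r = 25, 1.15 at r = 26) and changes nothing else. Enumerating every pair (a, c) confirms this:

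| Responders per arm | Response | Lead needed, missing = use | Lead needed, complete case | Results that disagree |
|---|---|---|---|---|
| 30 | 100% | 2 | 2 | 0 of 961 |
| 26 | 87% | 2 | 2 | 0 of 729 |
| 25 | 83% | 2 | 2 | 0 of 676 |
| 21 | 70% | 2 | 2 | 0 of 484 |
| 20 | 67% | 2 | 1 | 20 of 441 |

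The agreement stops at 20 responders per arm, where a lead of 1 is 1/20 = 5.0% (met) against 1/30 = 3.3% (not met).

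**Step 2: unequal response or unequal arms.** Disagreement is possible here. At 26 app v 25 control responders, 7 of 702 results disagree; at 25 v 26, 18 of 702. With arms of 31/29 or 29/31 and 25 responders in each, 18 or 21 of 676 disagree. At 24 app v 27 control, a result of 3 v 2 gives 3/24 - 2/27 = 12.5% - 7.4% = +5.1 (met) under complete case and 1/30 = +3.3 (not met) under missing = use. Summing binomial probabilities over all disagreeing results at 24 v 27, with assumed true rates (control/app) of 5/10%, 10/10%, 10/15% and 15/20%, gives disagreement in about 7-14% of trials. In every case the cause is the denominators; the missing outcomes are never varied.

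**Step 3: can the missing decide the verdict?** Take 26 responders per arm (4 missing in each) and 5 v 3 abstainers.
- Missing = use: 5/30 - 3/30 = 16.7% - 10.0% = +6.7, met.
- Complete case: 5/26 - 3/26 = 19.2% - 11.5% = +7.7, met.
- One missing control abstinent, no missing app participant abstinent: 5/30 - 4/30 = 16.7% - 13.3% = +3.3, not met.

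If x missing app participants and y missing controls were abstinent, the difference is (2 + x - y)/30, and the criterion is met only when x ≥ y. Of the 5 × 5 = 25 combinations, 15 meet it and 10 do not.

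**Step 4: range of results open to reversal.** With m missing per arm, the observed lead can move by at most m either way, so some allocation reverses the verdict whenever 2 - m ≤ a - c ≤ 1 + m. That is -2 to +5 for m = 4 and -3 to +6 for m = 5. The outer values need extreme allocations. The planned analyses do not show where an observed result falls in this range.

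**The case against.** Four points can be made for the plan.

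1. **Exact agreement needs special conditions.** It requires a 30/30 split, which stratified permuted blocks do not guarantee, and equal responder counts. Assuming independent 85% response, counts are exactly equal in only about 14% of trials. A reader might infer that complete case can never disagree with missing = use. The figures do not support that: the two differ at 20 or fewer responders per arm and can differ when response is unequal. This limit stands, but it does not turn complete case into a check on missing outcomes.

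2. **Much of the fragility is not due to missing data.** A reader might count how often the lead among 25-26 responders is exactly 1 or 2, where one missing participant could reverse the verdict. That is 29-41% of trials at the assumed rates above, and it is tempting to call it the harm from missingness. With complete follow-up of 30 per arm, a lead of exactly 1 or 2 still occurs in about 27-39%. The figure mainly reflects how coarse a 5-point threshold is at this size.

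3. **The consequence is limited.** A reader might infer that the missing participants could overturn the go decision itself. Overall go also needs mean satisfaction of at least 3.5, and its efficacy part can be met through readiness to quit or quit attempts alone. The abstinence verdict decides the efficacy part only if both of those fall short.

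4. **This is a descriptive pilot with a cited convention.** The plan makes no claim of robustness and says itself that a small-sample effect estimate is unreliable. The example is also one-sided: one abstinent missing participant in each arm leaves +6.7. With the raw counts, a careful reader could work out the tipping point unaided.

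Points 2 to 4 limit how serious the gap is. They do not close it, because the threshold is still a stated criterion for proceeding and complete case is the only planned check on missing abstinence data.

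**Conclusion.** The concern holds within bounds. With 30 randomised per arm and equal response of at least 70%, complete case cannot disagree with missing = use on the abstinence criterion. Outside that case the two disagree rarely when counts are close, and in about 7-14% of trials at 24 app v 27 control responders under assumed rates of 5-20%. At no level of response does the comparison show whether the 8-9 participants expected to be missing decide the verdict, and in a result as ordinary as 5 v 3 a single one of them can.

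The agreement result is exact and rests only on the arm size, the 5-point threshold and equal responder counts. The disagreement percentages depend on assumed abstinence rates that the plan does not give. This is an inexpensive improvement to the analysis plan; it does not show that the go decision as a whole is unsound.

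**What to change.** In section 14.5 and DSMP 3.5, add a two-way tipping-point table for the abstinence endpoint. Rows run from 0 to the number of app participants with no survey or no cotinine result, and columns do the same for controls. Each cell assumes that many of them were abstinent, gives the resulting difference and marks whether it reaches 5 points. Report with it the smallest departure from missing = use that reverses the abstinence verdict. Keep complete case as a descriptive figure, and do not present its agreement with the primary rule as evidence of robustness.

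The cost is a few sentences and one table of about 6 by 6 cells at the expected response, with no new data or procedures. The downside is that a go on abstinence may be reported as less robust.
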